10.1.8 End Date

The stop date of the AE is the date at which the subject recovered, the event resolved but with sequelae or the subject died.

10.1.9 Pattern of Adverse Event

Episodic AEs (eg, vomiting) or those which occur repeatedly over a period of consecutive days are intermittent. All other events are continuous.

10.1.10 Action Taken with Study Drug

The action taken with the study drug should be defined using the following categories:

- Drug withdrawn – a study drug is stopped due to the particular AE.
- Dose not changed – the particular AE did not require stopping a study drug.
- Unknown – only to be used if it has not been possible to determine what action has been taken.

- Not Applicable – a study drug was stopped for a reason other than the particular AE eg, the study has been terminated, the subject died, dosing with study drug was already stopped before the onset of the AE, the AE that occurred before the study drug administration.

10.1.11 Outcome

- Recovered/Resolved – Subject returned to first assessment status with respect to the AE.
- Recovering/Resolving – the intensity is lowered by 1 or more stages: the diagnosis or signs/symptoms has almost disappeared; the abnormal laboratory value improved, but has not returned to the normal range or to baseline; the subject died from a cause other than the particular AE with the condition remaining “recovering/resolving”.
- Not recovered/Not resolved – there is no change in the diagnosis, signs or symptoms; the intensity of the diagnosis, signs/ symptoms or laboratory value on the last day of the observed study period has got worse than when it started; is an irreversible congenital anomaly; the subject died from another cause with the particular AE state remaining “Not recovered/not resolved”.
- Recovered/Resolved with sequelae – the subject recovered from an acute AE but was left with permanent/significant impairment (eg, recovered from a cardiovascular accident but with some persisting paresis).
- Fatal – the AEs which are considered as the cause of death.
- Unknown – the course of the AE cannot be followed up due to hospital change or residence change at the end of the subject’s participation in the study.

10.2 Procedures

10.2.1 Collection and Reporting of AEs

10.2.1.1 AE Collection Period

Collection of AEs will commence from the time the subject signs the informed consent. Routine collection of AEs will continue until the follow-up examination.

10.2.1.2 AE Reporting

At each study visit, the investigator or sub-investigator will assess whether any subjective AEs have occurred. A neutral question, such as “How have you been feeling since your last visit?” may be asked. Subjects may report AEs occurring at any other time during the study. Subjects experiencing a serious AE that occurs prior to the first exposure to study drug must be monitored until the symptoms subside and any clinically relevant changes in laboratory values have returned to baseline or there is a satisfactory explanation for the change. Non-serious AEs that occur prior to the first exposure to study drug, related or unrelated to the study procedure, need not to be followed-up for the purposes of the protocol.

All subjects experiencing AEs after the first exposure to study drug, whether considered associated with the use of the study drug or not, must be monitored until the symptoms subside and any clinically relevant changes in laboratory values have returned to baseline or until there is a satisfactory explanation for the changes observed. All AEs will be documented in the AE page of the eCRF, whether or not the investigator concludes that the event is related to the drug treatment. The following information will be documented for each event:

1. Event term.
2. Start and end date and time.
3. Pattern.
4. Severity.
5. Investigator's or sub-investigator's opinion of the causality between the event and administration of study drug(s) (related or not related).
6. Investigator's or sub-investigator's opinion of the causality to study procedure(s), including the details of the suspected procedure.
7. Action taken with study drug (not applicable for the AE that occurred before the study drug administration).
8. Outcome of event.
9. Seriousness.
10. Timing of occurrence (after administration of study drug)

10.2.2 Collection and Reporting of SAEs

When an SAE occurs through the AE collection period it should be reported according to the following procedure:

An SAE should be reported by the investigator or sub-investigator to the sponsor (see Annex) within 1 business day of the first onset or notification of the SAE, along with any relevant information. The investigator should submit the detailed SAE Form to the sponsor within 10 calendar days. The information should be completed as fully as possible but contain, at a minimum:

- A short description of the event and the reason why the event is categorized as serious.
- Subject identification number.
- Investigator's or sub-investigator's name.
- Name of the study drug(s).
- Causality assessment.

Any SAE spontaneously reported to the investigator or sub-investigator following the AE collection period should be reported to the sponsor if considered related to study participation.

10.2.3 Reporting of Abnormal Liver Function Tests

If a subject is noted to have ALT or AST $>3 \times \text{ULN}$ and total bilirubin $>2 \times \text{ULN}$ for which an alternative etiology has not been identified after the study drug administration in Period 1, the event (treatment-emergent only) should be recorded as an SAE and reported as per Section 10.2.2. The investigator or sub-investigator must contact the monitor for discussion of the relevant subject details and possible alternative etiologies, such as acute viral hepatitis A or B or other acute liver disease or medical history/concurrent medical conditions. Follow-up laboratory tests as described in Section 9.1.8 must also be performed.

10.3 Follow-up of SAEs

If information is not available at the time of the first report becomes available at a later date, the investigator or sub-investigator should complete a follow-up SAE form copy or provide other written documentation and submit it to the sponsor. Copies of any relevant data from the hospital notes (eg, ECGs, laboratory tests, discharge summary, postmortem results) should be sent to the addressee, if requested.

All SAEs should be followed up until resolution or permanent outcome of the event.

10.3.1 Safety Reporting to Investigators, IRBs, and Regulatory Authorities

The sponsor will be responsible for reporting all suspected unexpected serious adverse reactions (SUSARs) and any other applicable SAEs to regulatory authorities, investigators, IRBs, and the head of the study site. Relative to the first awareness of the event by/or further provision to the sponsor or sponsor's designee, SUSARs will be submitted to the regulatory authorities as expedited report within 7 days for fatal and life-threatening events and 15 days for other serious events, unless otherwise required by national regulations. The sponsor will also prepare an expedited report for other safety issues where these might materially alter the current benefit-risk assessment of the study drug/sponsor supplied drug or that would be sufficient to consider changes in the administration of the study drug/sponsor supplied drug or in the overall conduct of the trial. The study site also will forward a copy of all expedited reports to his or her IRB.

11.0 STUDY-SPECIFIC COMMITTEES

No steering committee, data safety monitoring committee, or clinical endpoint committee will be used in this study.

12.0 DATA HANDLING AND RECORDKEEPING

The full details of procedures for data handling will be documented in the Data Management Plan. AEs, medical history including concurrent medical conditions will be coded using the Medical Dictionary for Regulatory Activities (MedDRA). Drugs will be coded using the World Health Organization (WHO) Drug Dictionary.

12.1 Case Report Forms (Electronic)

Completed eCRFs are required for each subject who signs an informed consent.

The sponsor or its designee will supply study sites with access to eCRFs. The sponsor will make arrangements to train appropriate site staff in the use of the eCRF. These forms are used to transmit the information collected in the performance of this study to the sponsor and regulatory authorities. eCRFs must be completed in English. Data are transcribed directly onto eCRFs.

Corrections are recorded in an audit trail that captures the old information, the new information, identification of the person making the correction, the date the correction was made, and the reason for change.

The investigator must review the eCRFs for completeness and accuracy and must e-sign the appropriate eCRFs as indicated. Furthermore, the investigator must retain full responsibility for the accuracy and authenticity of all data entered on the eCRFs.

The following data will not be recorded directly into the eCRFs.

- Laboratory results
- Measurement results of drug concentrations

After the lock of the study database, any change of, modification of or addition to the data on eCRFs should be made by the investigator or sub-investigator with use of change and modification records of eCRFs (Data Clarification Form) provided by the sponsor.

eCRFs will be reviewed for completeness and acceptability at the study site during periodic visits by the sponsor or its designee. The sponsor or its designee will be permitted to review the subject's medical and hospital records pertinent to the study to ensure accuracy of the eCRFs. The completed eCRFs are the sole property of the sponsor and should not be made available in any form to third parties, except for authorized representatives of appropriate governmental health or regulatory authorities, without written permission of the sponsor.

12.2 Record Retention

The investigator and the head of the study site agree to keep the records stipulated in Section 12.1 and those documents that include (but are not limited to) the study-specific documents, the identification log of all participating subjects, medical records, source worksheets, all original signed and dated informed consent forms, electronic copy of eCRFs, including the audit trail, and detailed records of drug disposition to enable evaluations or audits from regulatory authorities, the sponsor or its designees. The investigator and the head of the study site are required to retain

essential relevant documents until the day specified as 1) or 2) below, whichever comes later. However, if the sponsor requests a longer time period for retention, the head of the study site should discuss how long and how to retain those documents with the sponsor.

1. The day on which marketing approval of the study drug is obtained (or the day 3 years after the date of notification in the case that the investigation is discontinued).
2. The day 3 years after the date of early termination or completion of the study.

In addition, the investigator and the head of the study site should retain the essential relevant documents until the receipt of a sponsor-issued notification to state the retention is no longer required.

13.0 STATISTICAL METHODS

13.1 Statistical and Analytical Plans

The statistical analysis plan (SAP) will be prepared and finalized prior to the database lock for interim analysis. This document will provide further details regarding the definition of analysis variables and analysis methodology to address study objectives.

13.1.1 Analysis Sets

In this study, two kinds of analysis sets are defined: pharmacokinetic analysis set and safety analysis set. The pharmacokinetic analysis set is defined as “all subjects who received the study drug, completed the minimum protocol-specified procedures without any major protocol deviations, and were evaluable for pharmacokinetics.” The safety analysis set is defined as “all subjects who received the study drug.”

13.1.2 Analysis of Demographics and Other Baseline Characteristics

Main demographics and other baseline characteristics will be summarized overall and by treatment group using the pharmacokinetic analysis set and the safety analysis set.

13.1.3 Pharmacokinetic Analysis

The following statistical analyses will be performed on the pharmacokinetic analysis set.

1. Plasma drug concentrations

For plasma concentration of TAK-536, descriptive statistics will be provided by visit for each formulation (TAK-536 commercial formulation, TAK-536 pediatric formulation). In addition, the plasma concentration-time profiles will be also provided.

For pharmacokinetic parameters except $AUMC_{last}$ and $AUMC_{\infty}$, descriptive statistics will be provided. For the ratio between each formulation (TAK-536 pediatric formulation/TAK-536 commercial formulation) for pharmacokinetic parameters AUC_{48} and C_{max} , descriptive statistics will be provided.

2. Assessment of bio-equivalence on pharmacokinetic parameters

The difference in the least square means between formulations (TAK-536 pediatric formulation - TAK-536 commercial formulation) and the two-sided 90% confidence interval (CI) will be provided using a crossover analysis of variance (ANOVA) model. The ANOVA model will include log-transformed (natural log) pharmacokinetic parameters AUC_{48} and C_{max} as dependent variable, and formulation, group, and period as independent variables. For log-transformed (natural log) pharmacokinetic parameters AUC_{last} , AUC_{∞} , $MRT_{\infty,ev,\lambda_z}$, and non-natural log transformed t_{max} , same analyses will be performed.

3. Methods of data transformation and handling of missing data

Details will be described in the Statistical Analysis Plan.

4. Significance level, confidence coefficient

- Significance level: 5% (one-sided test, assessment of bio-equivalence)
5% (two-sided test, other than assessment of bio-equivalence)
- Confidence coefficient: 90% (two-sided, assessment of bio-equivalence)
95% (two-sided, other than assessment of bio-equivalence)

5. Interpretation of bio-equivalence assessment

The bio-equivalence of the formulations (TAK-536 commercial formulation and TAK-536 pediatric formulation) will be evaluated according to the criteria set forth in the Guideline for Bioequivalence Studies of Generic Products [9]. The formulations will be considered bioequivalent if the 90% CIs (two-sided) of the differences in the means of the natural log-transformed AUC_{48} and C_{max} of TAK-536 between the TAK-536 commercial formulation and the TAK-536 pediatric formulation fall within the range of $\ln(0.80) - \ln(1.25)$.

When the 90% CIs will not fall within the range of $\ln(0.80) - \ln(1.25)$ with an add-on subject study, the formulations will be considered bioequivalent if the differences in the means of the natural log-transformed parameters AUC_{48} and C_{max} of TAK-536 between the TAK-536 commercial formulation and the TAK-536 pediatric formulation fall within the range of $\ln(0.90) - \ln(1.11)$, and the results of the dissolution test meet the conditions specified in the Guideline for Bioequivalence Studies of Generic Products. However, above provision will be applicable only if a combined number of subjects in this study and an add-on subject study is 30 subjects or greater.

13.1.4 Safety Analysis

The following statistical analyses will be performed on the safety analysis set.

1. Adverse events (treatment emergent adverse events)

A treatment emergent adverse event (TEAE) is defined as an event whose date of onset occurs on or after the start of study drug.

TEAEs will be coded using the MedDRA dictionary. The frequency distribution will be provided using the system organ class and the preferred term for each treatment as follows:

- All TEAEs
- Drug-related TEAEs
- Intensity of TEAEs
- Intensity of drug-related TEAEs
- TEAEs leading to study drug discontinuation
- Serious TEAEs

2. Laboratory test results, resting 12-lead ECGs, and vital signs (sitting blood pressure, sitting pulse [beats per minute], and body temperature), weight

For continuous variables, the observed values and the changes from baseline will be summarized by treatment for each visit using descriptive statistics. Case plots for the observed values will also be provided for each treatment.

For categorical variables, shift tables showing the number of subjects in each category at baseline and each post-baseline visit will be provided for each treatment.

13.2 Interim Analysis and Criteria for Early Termination

Interim analysis will be conducted due to judgment of necessity of an add-on subject study for the bioequivalence for TAK-536 commercial formulation and TAK-536 pediatric formulation.

13.2.1 Timing of Interim Analysis

An interim analysis will be performed after the database lock for the total of 14 subjects (7 per sequence).

13.2.2 Statistical Analysis Plan for Interim Analysis

The interim analysis will be the same analysis in [13.1.3.2](#). The further details are described in the SAP finalized prior to the database lock for interim analysis.

13.3 Determination of Sample Size

A total of 14 subjects (7 per sequence)

In case an add-on subject study is conducted, the maximum number of subjects will be 120 (60 per sequence).

[Rationale for the sample size]

Based on the currently available results of the studies conducted to date, the residual sum of squares of pharmacokinetic parameters C_{max} and AUC_{48} in the present study was assumed to be 0.13 and 0.08, respectively. For 6 subjects per sequence (total of 12 subjects per formulation), in two one-sided t-tests [$H_0: \ln(\mu) \leq \ln(\theta_1), \ln(\mu) \geq \ln(\theta_2)$; $H_1: \ln(\theta_1) < \ln(\mu) < \ln(\theta_2)$; where $\mu = \mu_t / \mu_s$, μ_t was the population mean for the pediatric formulation, μ_s was the population mean for the TAK-536 commercial formulation, $\theta_1 = 0.80$, and $\theta_2 = 1.25$] with a one-sided significance level of 5% and alternative hypothesis $\mu = 0.95$, more than 90% power of simultaneous detection of the bio-equivalence for pharmacokinetic parameters C_{max} and AUC_{48} . Taking into account possible occurrence of dropouts during the study and feasibility, 7 subjects per sequence (total of 14 subjects per formulation) were set.

In case bio-equivalence cannot be demonstrated with the number of subjects initially planned on account of insufficient subjects, an add-on subject study will be conducted in accordance with the Guideline for Bioequivalence Studies of Generic Products [\[9\]](#). The maximum number of subjects in the add-on subject study is 120 (60 per sequence), which is determined based on study feasibility, but is not on statistical consideration. The number of subjects in the add-on subject study will be determined based on the result of the interim analysis in this study and the currently available results of the studies conducted to date.

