## **6.0 DETERMINATION OF SAMPLE SIZE**

A total of 14 subjects (7 per sequence)

In case an add-on subject study is conducted, the maximum number of subjects will be 120 (60 per sequence).

[Rationale for the sample size]

Based on the currently available results of the studies conducted to date, the residual sum of squares of pharmacokinetic parameters  $C_{max}$  and  $AUC_{48}$  in the present study was assumed to be 0.13 and 0.08, respectively. For 6 subjects per sequence (total of 12 subjects per formulation), in two one-sided t-tests [ $H_0: \ln(\mu) \leq \ln(\theta_1), \ln(\mu) \geq \ln(\theta_2)$ ;  $H_1: \ln(\theta_1) < \ln(\mu) < \ln(\theta_2)$ ; where  $\mu = \mu_t / \mu_s$ ,  $\mu_t$  was the population mean for the pediatric formulation  $\mu_s$  was the population mean for the TAK-536 commercial formulation,  $\theta_1 = 0.80$ , and  $\theta_2 = 1.25$ ] with a one-sided significance level of 5% and alternative hypothesis  $\mu = 0.95$ , more than 90% power of simultaneous detection of the bio-equivalence for pharmacokinetic parameters  $C_{max}$  and  $AUC_{48}$ . Taking into account possible occurrence of dropouts during the study and feasibility, 7 subjects per sequence (total of 14 subjects per formulation) were set.

In case bio-equivalence cannot be demonstrated with the number of subjects initially planned on account of insufficient subjects, an add-on subject study will be conducted in accordance with the Guideline for Bioequivalence Studies of Generic Products [1]. The maximum number of subjects in the add-on subject study is 120 (60 per sequence), which is determined based on study feasibility, but is not on statistical consideration. The number of subjects in the add-on subject study will be determined based on the result of the interim analysis in this study and the currently available results of the studies conducted to date.

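### Does calling the planning variability a residual sum of squares undermine the 14-subject sample size?

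*Protocol*

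**What the plan says.** Protocol Section 13.3 states that "the residual sum of squares of pharmacokinetic parameters C_{max} and AUC_{48} in the present study was assumed to be 0.13 and 0.08" respectively, drawing on earlier studies. The next sentence begins "For 6 subjects per sequence (total of 12 subjects per formulation" and claims "more than 90% power of simultaneous detection of the bio-equivalence for pharmacokinetic parameters". The test is two one-sided t-tests at 5%, limits 0.80 and 1.25, true ratio 0.95. Enrolment is then set at 14 (7 per sequence) to allow for dropouts and feasibility.

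The sample-size justification in Protocol Section 2.0 says the same. Section 6.0 of both the final and the interim SAP repeats the label, "the residual sum of squares of pharmacokinetic parameters". None of these places gives residual degrees of freedom, the size of the earlier studies, or a standard deviation, variance or CV for the two figures.

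On a possible add-on study, Section 13.3 says "The number of subjects in the add-on subject study will be determined based on the result of the interim analysis in this study", together with the available results of earlier studies. The cap of 120 subjects is stated to rest on feasibility, not on statistics.

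**The concern.** The power of two one-sided tests in a crossover depends on the within-subject residual standard deviation. A residual sum of squares grows with the number of subjects and says nothing about precision until it is divided by its degrees of freedom. As labelled, the input can neither produce nor confirm the stated power.

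The reading matters. As standard deviations the figures reproduce the claim closely. As residual variances, the nearest other quantity in an ANOVA table, they give almost no power at 12 subjects. It is then tempting to conclude that the planning input is wrong. These are the only variability figures behind the sample size, and earlier study results are also to inform the size of any add-on. If someone carried 0.13 and 0.08 forward as mean squares, an add-on could come out several times too large.

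**Working it through.** **Inputs** (Protocol 13.3): limits ln(0.80) = −0.2231 and ln(1.25) = 0.2231; true difference ln(0.95) = −0.0513; one-sided 5%; N = 12 in a 2×2 crossover, so residual df = N − 2 = 10.

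**Formula.** The standard error of the formulation difference is SE = s·√(2/N), where s is the within-subject residual SD on the ln scale. Equivalence is shown when the estimate ± t(0.95, N−2)·SE lies inside the limits. Power is the probability of this, integrated over the chi-square distribution of the estimated residual variance. Joint power is taken as the product of the two endpoint powers.

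**The plan's own figure, reading 0.13 and 0.08 as SDs.**
- Cmax: SE = 0.13 × √(2/12) = 0.0531. The nearer limit is 0.2231 − 0.0513 = 0.1718 away, which is 3.24 SE. Power is 91.3%; simulation gives 91.4%.
- AUC48: SE = 0.08 × √(2/12) = 0.0327, a distance of 5.26 SE. Power is 99.9%.
- Joint: 0.913 × 0.999 = 0.912. The lower bound that needs no independence assumption, 0.913 + 0.999 − 1, is also 0.912.
- At N = 10 the joint power is 84.6%, at N = 11 88.1%, and at the enrolled N = 14 95.0%.

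The claim of more than 90% at 12 therefore reproduces, with no unstated quantity.

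**Other readings.** For a literal sum of squares, s = √(SS/df), with df an assumption because the documents give none. At df = 8, for example, s = √(0.13/8) = 0.1275 for Cmax and √(0.08/8) = 0.100 for AUC48.

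| Reading of 0.13 / 0.08 | s for Cmax / AUC48 | Joint power, N = 12 | Smallest even N above 90% |
|---|---|---|---|
| Residual SD | 0.130 / 0.080 | 91.2% | 12 |
| CV, s = √ln(1 + CV²) | 0.129 / 0.080 | 91.4% | 12 |
| Residual variance | 0.361 / 0.283 | 0.8% (Cmax alone 4.5%) | 82 |
| Variance of the difference, s = √(value/2) | 0.255 / 0.200 | 15.3% | 42 |
| Sum of squares, df 4 | 0.180 / 0.141 | 57.8% | 22 |
| Sum of squares, df 6 | 0.147 / 0.115 | 80.5% | 16 |
| Sum of squares, df 7 | 0.136 / 0.107 | 86.8% | 14 |
| Sum of squares, df 8 | 0.127 / 0.100 | 91.1% | 12 |
| Sum of squares, df 9 | 0.120 / 0.094 | 94.0% | 12 |
| Sum of squares, df 10 | 0.114 / 0.089 | 95.9% | 10 |
| Sum of squares, df 12 | 0.104 / 0.082 | 98.2% | 10 |

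Two things follow. First, the SD reading is not the only one that fits. A sum of squares with 8 or 9 df, as from a 2×2 crossover of 10 or 11 subjects (df = N − 2), gives more than 90% at 12 and less at 10. The protocol says only that 12 subjects give more than 90%, not that 12 is the smallest such number; on that statement every df of 8 or more agrees. Second, the readings that fail clearly are those as variances, and no section uses that word for these figures.

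**Does the label reach any later step?** The bioequivalence rule (Protocol 13.1.3, SAP 7.8.4.6) uses the 90% confidence interval computed from the observed data, so the planning figure does not enter it. For the add-on, the interim crossover ANOVA supplies its own residual with its df. With 14 completers (df = 12) and a true Cmax SD of 0.13, that analysis would be expected to show a mean square near 0.13² = 0.0169 and a sum of squares near 12 × 0.0169 = 0.203. A planning value of 0.13 misread as a mean square would be 0.13 / 0.0169 = 7.7 times too large beside that output, and the mismatch would be plain.

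**The case for a change.** The best case for a change is that a protocol should state its planning input so that a reader can check it, and this one does not. The documents omit the df that a sum of squares needs. The same label stands in the protocol summary, Protocol 13.3 and both SAPs. Neither SAP gives a formula for sizing the add-on, and earlier study results, the stated source of 0.13 and 0.08, are named as an input to that sizing. A statistician who took the figures as mean squares would arrive at 82 subjects where 12 suffice. The correction costs a few words.

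Part of this stands. The input is mislabelled or incompletely specified, and as labelled it cannot be verified. The rest does not carry. The mis-sizing needs a variance reading that the text does not suggest, and it would have to survive comparison with the interim residual. The documents also do not say that 0.13 and 0.08 themselves will be reused. Nor can the replacement wording be settled from outside: SD is the likeliest meaning, but a sum of squares with 8 or 9 df fits the plan's statement too, and writing SD without the sponsor's calculation record could itself introduce an error.

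**Conclusion.** The label is at fault, very probably a slip for residual standard deviation; the sample size is not shown to be wrong. On the SD reading the stated power is reproduced at 91.2% for 12 subjects, and the 14 enrolled give 95.0%. Naming the quantity correctly would leave the sample size, the stated power, the analysis and the bioequivalence decision where they are. This is a clerical matter that the sponsor can settle from its own calculation record, and no change to the plan follows.

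The conclusion assumes that the figures were used as SDs, as CVs, or as sums of squares with at least 8 df. It would change if the sponsor's record showed variances, or a sum of squares on fewer than 8 df, because the stated power at 12 subjects would then not hold. It also assumes that any add-on is sized from the within-subject residual of the interim crossover analysis, which is how a statistician would ordinarily do it.
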